8.1 Definition of an adverse event

An AE is any untoward medical occurrence in a subject or clinical investigation subject administered a pharmaceutical product that does not necessarily have a causal relationship with this treatment. An AE can therefore be any unfavorable and unintended sign (including an abnormal laboratory finding, for example), symptom, or disease temporally associated with the use of study medication, whether or not considered related to the study medication.

8.2 Definition of a serious adverse event

An SAE is defined as any untoward medical occurrence that at any dose:

- Results in death.
- Is life-threatening.
- Requires hospitalisation or prolongation of existing hospitalisation.
- Results in persistent or significant disability or incapacity.
- Is a congenital anomaly or birth defect.
- Is an important medical event.

Medical and scientific judgment should be exercised in deciding whether an AE is serious and whether expedited reporting is appropriate in other situations, such as important medical events that may not be immediately life-threatening or result in death or hospitalization but may jeopardize the subject or may require medical or surgical intervention to prevent 1 of the other outcomes listed in the above definition. These should also be considered serious. Examples of such events are invasive or malignant cancers, intensive treatment in an emergency room or at home for allergic bronchospasm, blood dyscrasias or convulsions that do not result in hospitalization, or development of drug dependency or drug abuse. These should also usually be considered serious.

The term 'life-threatening' refers to an event/reaction in which the subject was at risk of death at the time of the event/reaction; it does not refer to an event/reaction which hypothetically might have caused death if it were more severe.

Admission to a hospital as a new inpatient is deemed as meeting this criterion, even when the length of hospital stay was less than 24 hours. Transfer to other departments of the same hospital due to a newly emerged event during the hospitalization (e.g., transfer from the psychiatry ward to the internal medicine ward, from the internal medicine ward to the coronary intensive care unit, or from the neurology ward to the tuberculosis ward) is also counted as hospitalization.

SAEs will be recorded and reported as described in Section 8.7.

8.3 Severity of adverse events

The severity of AEs will be classified according to the following criteria:

Mild: The event is transient and easily tolerated by the subject.

Moderate: The event causes discomfort and interferes with the subject's general condition.

Severe: The event causes considerable interference with the subject's general condition and may be incapacitating.

To ensure no confusion or misunderstanding of the difference between the terms 'serious' and 'severe', which are not synonymous, the following note of clarification is provided:

The term 'severe' is often used to describe the severity of a specific event (as in mild, moderate, or severe myocardial infarction); the event itself, however, may be of relatively minor medical significance (such as severe headache). This is not the same as 'serious', which is based on patient/event outcome or action criteria usually associated with events that pose a threat to a patient's life or functioning. Seriousness (not severity) serves as a guide for defining regulatory reporting obligations.

8.4 Relationship of adverse events to Investigational Medicinal Product

The causal relationship of the AE to study medication will be determined as either 'reasonable possibility' or 'no reasonable possibility', defined as:

Reasonable Possibility – The relationship of the clinical event to the study medication makes a causal relationship possible, and other drugs, therapeutic interventions, or underlying conditions do not provide a sufficient explanation for the observed event.

No Reasonable Possibility – The relationship of the clinical event to the study medication makes a causal relationship unlikely, or other drugs, therapeutic interventions or underlying conditions provide a sufficient explanation for the observed event.

8.5 Clinical laboratory abnormalities and other abnormal assessments

8.5.1 Clinical laboratory abnormalities

The Investigator will exercise medical judgment in deciding whether abnormal laboratory values are clinically significant. Laboratory abnormalities which are judged by the Investigator to be clinically significant will be recorded as AEs.

If an abnormal laboratory value or assessment is clearly related to a medically-defined diagnosis or syndrome, the diagnosis or syndrome will be recorded on the AE form, not the individual laboratory values.

All clinically significant abnormal laboratory results or assessments will be followed until they resolve (return to normal or baseline values) or stabilize, or until they are judged by the Investigator to be no longer clinically significant. Repeat laboratory tests or measurements will be performed for abnormal results.

8.6 Recording and reporting of adverse events

All AEs, regardless of the relationship to study medication, occurring from the time written informed consent is obtained from a subject through the EOS/Follow-up visit or subject early withdrawal from the study, and any AEs or SAEs reported spontaneously through the end of the Safety Follow-up period, should be reported to the Sponsor or designee.

NOTE: Elective hospitalization or procedure/surgery planned before subject enrollment for a preexisting medical condition does not constitute an AE unless the underlying disease or condition worsens after signing informed consent.

At each study visit, after the subject has had an opportunity to spontaneously mention any problems, the Investigator should inquire about the occurrence of AEs. The questioning should be open-ended and non-leading.

All AEs will be recorded on an AE form in the eCRF. Reports should contain a description of the event, date and time of onset, date and time of resolution, severity, treatment required, relationship to study medication, action taken with the study medication, outcome and whether the event is classified as serious.

The Investigator will evaluate the severity of the AEs (as defined in Section 8.3) and will assess the causality between the AEs and the study medication (as defined in Section 8.4).

Pre-existing illnesses, which started prior to study entry and are still ongoing at the start of the study, will not be considered AEs unless they worsen during the treatment period. Pre-existing conditions will be recorded as medical history.

If the Investigator becomes aware of any new safety information, or any safety information which appears to be either study or study medication related after the Safety Follow-up period, then they must notify the Sponsor or designee immediately.

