5.2.2 Follow-up

5.2.2.1 Visit 7: Follow-up Visit (FU, Week 68 or 4 weeks after early termination)

Subjects who complete the study (or subjects who withdraw from treatment early) will be telephoned by the Investigator (or designee) 30 days after EOT, for a Follow-up visit. Information on any new AEs, follow-up on existing AEs, and prior/concomitant medication will be recorded.

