8 ADVERSE EVENT MANAGEMENT

All AEs and SAEs will be recorded in the source documents. All AEs and SAEs that occur from the time the informed consent is signed until the end of the Safety Follow-up period (30 days after the last treatment visit) will be recorded in the eCRF. Even if the AE is assessed by the Investigator as not related to study medication, its occurrence must be recorded in the source documents and eCRF. AEs will be classified as 'treatment-emergent' if they arise following the first administration of study medication in the OLE period or if an AE which is continued from the preceding trial (Study MT-8554-A01) increases in severity following the first administration of study medication in the OLE period.

At each study visit, after the subject has had an opportunity to spontaneously mention any problems, the Investigator should inquire about the occurrence of AEs. The questioning should be open-ended and non-leading.

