10.3.4.1 Adverse events

AEs are considered as treatment emergent if they occur after the first dose administration of study medication of Study MT-8554-A02 or if a pre-dose event increases in severity following dosing. The frequency and incidence of TEAEs will be summarized by System Organ Class (SOC) and Preferred Term (PT), by treatment group and overall. TEAEs will be summarized by treatment, by relationship to study medication and by maximum severity as well. Serious TEAEs and TEAEs leading to study medication discontinuation will be summarized in tables. All AE will be presented in a data listing.

Physical examination data will be listed by subject. Changes in physical examinations will be described in the text of the CSR.

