## **7.3.2 Safety Assessments**

### **7.3.2.1 Adverse events (AEs)**

An AE is any untoward medical occurrence in a subject or clinical investigation subject administered a pharmaceutical product that does not necessarily have a causal relationship with this treatment.

AEs will be coded using Medical Dictionary for Regulatory Activities (MedDRA) central coding dictionary, Version 20.1.

Treatment-emergent AEs (TEAEs) are defined as AEs that started or worsened in severity on or after the first dose of study medication. The treatment relationship with the AE is in 2 categories (reasonable possibility, no reasonable possibility). The detail is included in protocol.

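### Protocol 8.6 counts worsening of a pre-existing illness as an AE only in the treatment period, which conflicts with the recording window that runs to the end of Safety Follow-up

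*Protocol*

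**What the plan says.** Protocol 8.6 states that illnesses which began before study entry and are still ongoing at the start "will not be considered AEs unless they worsen during the treatment period"; they are otherwise recorded as medical history. Protocol 5.2.1.3 describes Visit 6 (Week 64 or early termination) as the last visit of the treatment period. Table 1 and Protocol 5.2.2 place Visit 7, a telephone call 30 days after end of treatment, in a separate Follow-up period.

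Other sections set a wider window:

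- Protocol 8 requires eCRF recording of "All AEs and SAEs that occur from the time the informed consent is signed until the end of the Safety Follow-up period", which it puts at 30 days after the last treatment visit. An AE carried over from Study A01 is treatment-emergent if it "increases in severity following the first administration of study medication in the OLE period", with no end date.
- The first paragraph of Protocol 8.6 covers AEs from consent through the EOS/Follow-up visit or early withdrawal.
- Protocol 8.7 requires SAEs to be reported from consent to the end of Safety Follow-up or withdrawal, with no exception for pre-existing illness.
- Protocol 10.3.4.1 treats an event as treatment-emergent "or if a pre-dose event increases in severity following dosing". SAP 7.3.2.1 does the same for "AEs that started or worsened in severity on or after the first dose of study medication".
- The NOTE in Protocol 8.6 on planned elective procedures exempts them "unless the underlying disease or condition worsens after signing informed consent".

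At the Visit 7 call, "Information on any new AEs, follow-up on existing AEs, and prior/concomitant medication will be recorded".

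**The concern.** Long-term safety is the primary objective, and Protocol 4.6 says that all subjects are followed for 30 days for AEs. After Visit 6 the only scheduled contact is the telephone call. Vital signs, ECG, laboratory tests, PHQ-8 and GAD7 are last listed at Visit 6, and the VMS diary is collected there. AE recording is therefore the only scheduled route by which worsening after that visit can reach the database.

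The sections that set the window speak of AEs and SAEs, whereas the sentence in 8.6 decides whether a worsened pre-existing illness is an AE at all. A coordinator who applies 8.6 faithfully could leave such an event out, while a colleague at another site who applies section 8 would enter it. The same clinical course would then give different records at different sites. Pre-existing conditions are expected in this population: SAP 8.1.2 tabulates hypertension, heart failure, diabetic status and antidepressant use at baseline.

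**Working it through.** The plan gives no figure for this point, so the check is a comparison of text, followed by simple arithmetic for the length of the window.

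**Step 1: when the treatment period ends.** Protocol 5.2.1.3 ends it at Visit 6. Visit 7 is a separate Follow-up visit in 5.2.2.1 and in Table 1. The interval in question is Visit 6 to Visit 7.

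**Step 2: what each rule does with a medical-history condition that first worsens in that interval.**

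| Place | Role | Start | End | Is the event covered? |
|---|---|---|---|---|
| Protocol 8.6, pre-existing illness | Decides what is an AE | Treatment period | Visit 6 | No, read literally |
| Protocol 8 | Recording | Consent | End of Safety Follow-up | Yes, if it is an AE |
| Protocol 8.6, first paragraph | Reporting | Consent | EOS/Follow-up visit or withdrawal | Yes, if it is an AE |
| Protocol 8.7 with 8.2 | SAE reporting | Consent | End of Safety Follow-up or withdrawal | Yes, if serious |
| Protocol 10.3.4.1 | Classification | First A02 dose | None stated | Yes, once recorded |
| SAP 7.3.2.1 | Classification | First dose | None stated | Yes, once recorded |

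**Step 3: non-serious worsening.** Section 8 depends on the event being an AE, and 8.6 says that it is not. The general AE definition in 8.1 has no such exception, so the sentence in 8.6 alone creates the gap.

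**Step 4: serious worsening.** Protocol 8.2 defines an SAE by the medical occurrence and its seriousness, without an exception for pre-existing illness, and 8.7 requires a report within 24 hours. The 8.6 sentence points the other way. The site has two instructions that do not agree.

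**Step 5: whether the analysis can repair it.** SAP 7.1 uses observed data, and its TEAE rule for incomplete dates applies only to events already in the database. An unrecorded event is lost. SAP section 10, on changes from the protocol, does not address the point.

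**Step 6: length of the window.**

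- Planned treatment: 52 × 7 = 364 days. Follow-up: 30 days.
- Share of planned observation per completer: 30 / (364 + 30) = 30 / 394 = 7.6%.
- For about 100 completers: 100 × 30 = 3,000 subject-days; 3,000 / 365.25 = 8.2 person-years.
- If all 364 planned subjects had a follow-up call: 364 × 30 = 10,920 subject-days; 10,920 / 365.25 = 29.9 person-years.
- Table 1 places the visits at Days 448 and 476, which gives 476 − 448 = 28 days. The text says 30 days.

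These figures size the window only. The documents give no rate of worsening after treatment, so no count of missed events follows from them.

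**The case against.** The strongest reply is that one loosely worded sentence should not be read as overriding the general windows in Protocol 8, 8.6 and 8.7. Much of this stands:

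- New symptoms and diagnoses are captured at Visit 7, and existing AEs are followed up there and under Protocol 8.10. Section 8 deals expressly with AEs continuing from A01. What remains is a medical-history condition, not already an AE, that first worsens in about 30 days.
- Protocol 10.3.4.1 and SAP 7.3.2.1 classify events for tabulation and do not tell sites what to record. They show that the analysis expects a wider class of events than 8.6 admits, and no more.
- The NOTE in 8.6 is a rule for planned procedures. It shows a different reference point within the same section, but it does not govern worsening in general.
- Protocol 10.3.4 describes the safety analysis as covering the open-label period, and no objective concerns withdrawal or rebound effects.

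A reader might infer that worsening after MT-8554 is stopped, even if serious, goes unrecorded. The documents do not support that. Serious worsening still meets 8.2 and 8.7. Stopping drug is also not the same as leaving the treatment period: Protocol 4.5.1 asks that women who stop drug stay on study through the final visit, and the term is not defined for them. Nor do the documents say that the return of VMS after treatment is an AE, so it cannot be assumed that every woman has an excluded event.

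The reply does not remove the conflict. Section 8.6 is the place that says which worsened illnesses are AEs, and its limit is narrower than the window stated in its own first paragraph.

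**Conclusion.** The inconsistency is real and narrow. Read literally, 8.6 removes from the AE definition any worsening of a medical-history condition that first occurs between Visit 6 and the end of Safety Follow-up. That conflicts with Protocol 8, the first paragraph of 8.6 and 8.7, and it is narrower than the treatment-emergent definitions. For non-serious worsening the likely result is site-dependent under-recording; for serious worsening it is contradictory instruction, not settled exclusion.

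The affected window is about 30 days per woman, or 7.6% of planned observation for a completer. The number of events at stake is unknown. A worked example with an assumed event rate and nothing recorded might suggest a large bias, but it would need a rate that the documents do not give and would have to suppose that every site disregards section 8. The SAP text also plans no separate estimate of worsening after treatment.

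The conclusion rests on two readings: that the treatment period ends at Visit 6, as 5.2.1.3 indicates, and that sites may apply the 8.6 sentence as written.

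**What to change.** In the pre-existing-illness sentence of Protocol 8.6, replace the limit to the treatment period with *at any time from signed informed consent to the end of the Safety Follow-up period*. Starting at consent matches sections 8 and 8.7; starting at the first A02 dose would open a new mismatch at the front of the window. The first A02 dose should remain the start point for treatment-emergence only.

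In Protocol 5.2.2.1, state that the Visit 7 call records worsening of pre-existing conditions as AEs.

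The cost is one phrase in 8.6 and one line for the call. No visit or procedure is added. The small downside is a few more AE records. A SAP flag for events that begin or worsen after the last dose would let them be shown separately, but it is optional and not part of the correction.

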8.7 Recording and reporting of serious adverse events

All SAEs occurring from the time the informed consent is signed from the subject until the end of the Safety Follow-up period or the withdrawal of the subject from the study must be reported to the **Sponsor or designee** using the ***Serious Adverse Event (SAE) Form in Clinical Study within 24 hours*** of the Investigator becoming aware of the SAE. All SAEs must also be entered in the AE section of the eCRF **within 24 hours**.

The SAE report should be completed as thoroughly as possible, including an assessment of causality. All such reports will identify subjects by unique code numbers assigned to the study participants, rather than by the subjects' names, personal identification numbers, or addresses.

The designee reporting contact for SAEs is as follows:

Email: [REDACTED]

Fax: [REDACTED]

In case of any email problems, the SAE form will be sent to the Sponsor via email or fax to:

E-mail: [REDACTED]

Fax: [REDACTED]

Reports of pregnancy, although not classified as an SAE, will be handled and reported as in Section 8.9.

The Sponsor will comply with the applicable regulatory requirements related to the reporting of Suspected Unexpected Serious Adverse Reactions (SUSARs) to the regulatory authorities and central IRB(s) and will provide all SAEs to the regulatory authorities and Investigator. The Investigator will be responsible for informing the local IRB(s) of relevant safety information, including SUSARs, as per local laws and requirements.

8.8 Adverse events associated with endometrial safety assessments

A transvaginal ultrasound and endometrial biopsy will be performed for subjects with a uterus. These procedures will be performed to assess endometrial safety (endometrial thickness, as measured by transvaginal ultrasound, and incidence of endometrial hyperplasia, as measured by endometrial biopsy). The scans by ultrasound will be processed and assessed centrally. Biopsy samples will be processed and assessed by central laboratories. Biopsy results will be adjudicated by a committee consisting of 3 independent expert pathologists.

The Investigator will perform an overall evaluation of the transvaginal ultrasound results and endometrial biopsy report. The Investigator will exercise medical judgment in deciding whether abnormal results are clinically significant. Abnormalities which are judged by the Investigator to be clinically significant will be recorded as AEs.

If a subject has an abnormal endometrial stripe of ≥ 5 mm thickness as measured by transvaginal ultrasound performed at Week 12 and Week 64 or early termination, independent of the results of endometrial biopsy, the Investigator will be informed and advised to refer subject to a gynecologist for further management. Further management and the decision to conduct a hysteroscopy and dilatation/curettage will be deferred to the physician's opinion and the subject's acceptance.

8.9 Pregnancy

If a female subject who has been exposed to the study medication becomes pregnant, the course and outcome of the pregnancy should be monitored and documented.

Pregnancy occurring in a female subject who has been exposed to the study medication, although not classified as an SAE, must be reported using the same timelines and contact details as an SAE (Section 8.7) via a paper *Pregnancy Notification Form in Clinical Study* form. If the outcome or course of the pregnancy involves an SAE (e.g., a congenital anomaly or spontaneous abortion), then the *Serious Adverse Event (SAE) Form in Clinical Study* needs to be completed.

Subjects who become pregnant while on study should be withdrawn from treatment, as described in Section 4.5.1.

8.10 Follow up of adverse events

The Investigator should follow up subjects with AEs/SAEs, until the event has resolved or stabilized and any abnormal laboratory values have returned to baseline; or until there is a satisfactory explanation for the changes observed. In the case of death, if possible a pathologist's full report should be supplied.

8.11 Reference safety information

The reference safety information for this clinical study is the MT-8554 Investigator's Brochure².

8.12 Overdose

There is no known antidote for MT-8554. Any signs or symptoms of a possible overdose will be treated supportively. In the case of an emergency, standard emergency procedures and medical care will be given.

If the subject takes a dose which is greater or more frequent than that specified in the protocol (with or without associated symptoms), this overdose is an AE and must be reported to the Sponsor or the designee on the AE eCRF.

If the overdose meets serious criteria, the SAE must be reported to Sponsor or the designee immediately or within 24 hours of awareness using the *Serious Adverse Event (SAE) Form in Clinical Study* according to SAE reporting procedures (see Section 8.7).

If the subject experiences any associated symptoms as a result of the overdose, the Investigator will record this as a separate AE/SAE.

9 DATA COLLECTION AND PROCESSING

9.1 Data collection

Subject data will be collected on individual eCRFs and will be substantiated by source documents (such as laboratory reports, medical records or ECGs) at the Investigator site. All relevant data will be transcribed into the eCRF from source documents, entered into the study database directly from source documents, or transferred electronically to the study database. Where no printed or electronic source documents exist, data will be entered directly into the eCRF and the eCRF will be considered the source document.

Subjects will record the occurrence and severity of VMS on an ongoing basis using a VMS diary, which includes an electronic patient-reported outcome (PRO) instrument. The instrument will transmit data to a technology service provider database, where it will be stored as electronic source for efficacy endpoints. A paper back-up VMS diary card will be used in case of device malfunction, stolen or lost.

Prior to the start of the study, the Investigator will complete a Delegation of Responsibility List. The Sponsor or designee will provide training for completion of the eCRF. The eCRF will be completed according to guidelines provided by the Sponsor or its designee in writing, electronically, and/or verbally.

Completed eCRFs will be reviewed by the Study Monitor for the study to ensure data accuracy, completeness and consistency. Any discrepancies found during the eCRF review or during data validation and/or quality assurance reviews of the data by data management or other functions are to be clarified by the Investigator (or his/her designated personnel).

The Investigator or designee must record all required subject data using the previously specified data collection method defined by the Sponsor. An explanation must be documented for any missing data. The Investigator must electronically sign and date a declaration on the eCRF attesting to his/her responsibility for the quality of all data recorded, and that the data represents a complete and accurate record of each subject's participation in the study. The data collected in the eCRF will be returned to the Sponsor, and an electronic copy will be retained by the Investigator.

